3.5.1. Dose Interruptions and Delays

Dose interruptions may occur in the event of a treatment-related toxicity or a non-treatment-related issue (e.g., elective surgery). If toxicity is clearly attributed to one drug based on the known toxicity profile then one drug may be interrupted while the other is continued. If the toxicity cannot clearly be attributed to one drug, then dose interruption for both drugs will be implemented.

Appropriate follow-up assessments should be done until adequate recovery occurs as assessed by the Investigator. Criteria required before treatment can resume for repotrectinib are described in the dose modification guidelines for adverse events table ([Table 4](#)). The guidelines provided in [Table 4](#) are general guidelines for dose modifications due to toxicities that may arise from repotrectinib. The guidelines provided in the label for trametinib should be referenced and followed to manage toxicities (i.e., see Table 2 in [Mekinist® \[trametinib\] USPI 2020](#)).

Doses may be held as needed until toxicity resolution. Depending on when the AE is resolved, a treatment interruption may lead to the subject missing all subsequent planned doses within that same cycle or even to delay the initiation of the subsequent cycle.

If a treatment delay results from worsening of hematologic or biochemical parameters, the frequency of relevant laboratory assessments may be increased as clinically indicated.

If the AE that led to the treatment interruption recovers within the same cycle, then re-dosing in that cycle is allowed. Doses omitted for toxicity are not replaced within the same cycle. The need for a dose reduction at the time of treatment resumption should be based on the criteria defined in [Table 4](#) unless otherwise agreed to following discussion between the Investigator and the Medical Monitor.

In the event of a treatment interruption for reasons other than treatment-related toxicity (e.g., elective surgery) lasting \geq 14 days, treatment resumption must be discussed with the Medical Monitor.

All study visits (visit date calculations) are based off the Cycle 1 Day 1 visit date, regardless of dose interruptions, and evaluations are to be performed according to the Schedule of Activities ([Table 1](#)). Every effort should be made to maintain the tumor assessments scheduling as described in the Schedule of Activities.

Table 4: Repotrectinib Dose Modification Guidelines for Adverse Events (CTCAE v5.0)

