AST or ALT elevation	Continue at same dose level.	Continue at same dose level. Withhold current dose if concurrent CTCAE grade ≥ 2 total bilirubin elevation ($> 1.5 \times$ ULN).	Withhold current dose until resolves to Grade ≤ 1 .	Discontinue treatment permanently.
Prolonged QTc	Assess electrolytes and concomitant medications. Correct any electrolyte abnormalities, or hypoxia. Continue at the same dose level.	Assess electrolytes and concomitant medications. Correct any electrolyte abnormalities, or hypoxia. Continue at the same dose level.	Withhold dose Assess electrolytes and concomitant medications. Correct any electrolyte abnormalities, or hypoxia. Upon recovery to grade ≤ 1 : if no other cause for QTc prolongation is found or is considered drug-related resume treatment at 1 dose level lower.	Discontinue treatment.
Dizziness, ataxia, or muscular weakness	Continue at same dose level.	Withhold current dose until toxicity is grade ≤ 1 or has returned to baseline OR reduce by 1 dose level immediately ^{1,2}	Withhold dose until toxicity is grade ≤ 1 or has returned to baseline, then reduce by 1 dose level ^{1,2} and resume treatment	Withhold dose until toxicity is grade ≤ 1 or has returned to baseline, then reduce by 1 dose level ^{1,2} and resume treatment; or discontinue treatment as per the Investigator's discretion after discussion with Medical Monitor.

Toxicity	CTCAE Grade 1*	CTCAE Grade 2*	CTCAE Grade 3	CTCAE Grade 4
Weight gain	Continue at same dose level. Implement effective weight management strategy (dietary advice from a nutritionist and food intake counseling).	Dose interrupt or dose reduce ^{1,2} , if required.	Dose interrupt or dose reduce ^{1,2} , if required.	Not applicable.

Abbreviations: ALT = alanine aminotransferase; AST = aspartate aminotransferase; CNS = central nervous system; CTCAE = Common Terminology Criteria for Adverse Events, v5.0; ILD = interstitial lung disease; QTc = QT interval corrected for heart rate; ULN = upper limit of normal.

*Cycle will not be extended to cover for the missing doses. In cases where no specific dose adjustments for CTCAE Grade 1 or Grade 2 treatment-related toxicity are provided, Investigators should always manage their subjects according to their medical judgment, which may include dose reduction or interruption based on the particular clinical circumstances.

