6.13. Cardiac Safety Monitoring

6.13.1. Electrocardiogram

Triple lead (with a 10-second rhythm strip) tracings will be used for all ECGs. It is preferable that the machine used has a capacity to calculate the standard intervals automatically. At each timepoint, 3 consecutive ECGs will be performed at approximately 2 minutes apart to determine the mean QTc interval. See the Schedule of Activities ([Table 1](#)).

When coinciding with blood sample draws for PK, the ECG assessment should be performed prior to blood sample collection such that the blood sample is collected at the nominal time.

If the mean QTc is prolonged (> 500 msec [i.e., CTCAE Grade 3]), then the ECGs should be re-evaluated by a qualified person at the site for confirmation as soon as the finding is made, including verification that the machine reading is accurate. If manual reading verifies a QTc of > 500 msec, immediate correction for reversible causes (including electrolyte abnormalities,

hypoxia, and concomitant medications with the potential to prolong the QTc interval) should be performed. Study drug will be held until the QTc interval decreases to ≤ 500 msec. Subjects will then re-start the study drug if no other cause for QTc prolongation is found or is considered drug-related resume treatment at 1 dose level lower ([Table 4](#)). If the QTc interval has still not decreased to < 500 msec after 2 weeks, or if at any time a subject has a QTc interval > 515 msec or becomes symptomatic, the subject will be removed from the study. Additional triplicate ECGs may be performed as clinically indicated.

Prior to concluding that an episode of prolongation of the QTc interval is due to study drug, thorough consideration should be given to potential precipitating factors (e.g., change in subject clinical condition, effect of concurrent medication, electrolyte disturbance) including possible evaluation by a specialist. If subject experiences a cardiac or neurologic AE (specifically syncope, dizziness, seizures, or stroke), an ECG (triplicate) should be obtained at the time of the event.

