7.3. Subject Discontinuation and Withdrawal from Study

A subject may be discontinued from study treatment at any time if the subject, the Investigator, or the Sponsor Medical Monitor determine that it is not in the subject's best interest to continue on study. The following is a list of possible reasons for early discontinuation of study treatment:

- Disease progression (unless there is reasonable evidence of clinical benefit to justify continuation on treatment - which must be previously discussed with the Sponsor)
 - Subjects should remain on study treatment until there is confirmed radiographic progression
 - Subject may be allowed to continue repotrectinib or trametinib beyond RECIST-defined progression if, in the clinical judgment of the Investigator, the subject continues to derive clinical benefit from the study drug(s) (with approval from Turning Point Therapeutics; see [Section 7.4](#))
- Any adverse event (AE) that cannot be adequately managed with dose modifications, including dose interruption > 28 days (unless there is reasonable evidence of clinical benefit to justify continuation on the protocol—which must be previously discussed with Turning Point Therapeutics) ([Section 3.5](#))
- Protocol violation requiring discontinuation of study treatment
- Subject is not compliant with study procedures
- Lost to follow-up
- Subject withdrawal of consent for further treatment
- Turning Point Therapeutics' early termination of study. Reasons for terminating the study may include, but are not limited to, the following:
 - All enrolled subjects have discontinued study treatment
 - The incidence or severity of AEs in this or other studies indicates a potential health hazard to subjects
 - Subject enrollment is unsatisfactory

Data to be collected for the EOT visit are described in the Schedule of Activities ([Table 1](#)).

Subjects will be followed for at least 28 calendar days after the last dose of study drug (i.e., repotrectinib and trametinib). If a subject is discontinued from treatment due to an AE, the subject will be followed until the AE has resolved or stabilized as per [Section 8.4](#).

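### Section 6.13.1 allows restart after a Grade 3 QTc event while QTc may still be Grade 2, whereas Table 4 requires grade ≤ 1; Table 4 also leaves Grade ≥ 3 paresthesia without a rule

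*Combined protocol and SAP*

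**What the plan says.** **QTc in Section 6.13.1.** The section ties the alert threshold to a grade: "If the mean QTc is prolonged (> 500 msec [i.e., CTCAE Grade 3". It then sets the release rule: "Study drug will be held until the QTc interval decreases to ≤ 500 msec". The next sentence restarts the subject, one dose level lower when the event is drug-related, and cites Table 4. Removal follows under two further conditions. One is a time limit: "If the QTc interval has still not decreased to < 500 msec after 2 weeks". The other is a ceiling: "if at any time a subject has a QTc interval > 515 msec or becomes symptomatic, the subject will be removed from the study".

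**QTc in Table 4 (Section 3.5.1).** The Grade 3 cell of the Prolonged QTc row withholds the dose and permits resumption one level lower only "Upon recovery to grade ≤ 1". Grade 2 has its own column. The row does not mention the removal limits of Section 6.13.1.

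**Which text governs.** Section 3.5.1 states: "Criteria required before treatment can resume for repotrectinib are described in the dose modification guidelines for adverse events table".

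**Paresthesia in Table 4.** The general non-hematologic row excludes dizziness, ataxia and paresthesia. The separate neurologic row covers dizziness, ataxia and muscular weakness. The asterisk note, which leaves unlisted situations to the Investigator's judgment, is confined to Grades 1 and 2.

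**The concern.** A site handling a QTc alert is likely to open the ECG section. If it applies the msec sentence there, it can restart repotrectinib in a subject whose QTc is still Grade 2 after a Grade 3 event. Table 4 would keep that subject on hold. The issue is patient safety and consistent handling across sites.

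The paresthesia gap is of the same kind. At Grade 3 or above, sites have no stated recovery grade and no stated reduction step, so they may act differently on the same event.

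The QTc point concerns repotrectinib only. Trametinib toxicity is referred to its label, which is not part of the documents.

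**Working it through.** No plan figure has to be reproduced, so the check compares the texts.

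**1. What ≤ 500 msec means as a grade.** Section 6.13.1 sets Grade 3 at > 500 msec. Table 4 has a distinct Grade 2 column for QTc. So ≤ 500 msec means Grade 2 or lower. The msec boundary between Grades 1 and 2 is not in the documents and is not needed for this step.

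**2. Who reaches the restart rule.** Section 6.13.1 removes anyone above 515 msec or symptomatic. The restart rule therefore applies to asymptomatic subjects with 500 < peak QTc ≤ 515 msec.

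**3. The two rules side by side, for those subjects.**

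| QTc during the hold | Section 6.13.1 | Table 4, Grade 3 cell |
|---|---|---|
| > 500 msec | hold | hold |
| ≤ 500 msec, still Grade 2 | restart | hold |
| grade ≤ 1 | restart | resume |

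The instructions differ in one row.

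**4. The 2-week boundary inside Section 6.13.1.** Release needs QTc ≤ 500. Removal at 2 weeks applies when QTc is not < 500, that is, QTc ≥ 500. The overlap of ≤ 500 and ≥ 500 is the single value 500 msec, where one rule restarts the subject and the other removes the subject.

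**5. Paresthesia.** It is excluded from the general row and absent from the neurologic row, so no Table 4 row applies. Muscular weakness shows the reverse pattern: it is named in the neurologic row but not excluded from the general one, so it falls in both. This looks like a slip between two row labels. Elsewhere (footnote a of Table 2) dizziness, ataxia and paresthesia are grouped as criteria for moving to 160 mg BID. Outside the table, two general provisions still apply at Grade ≥ 3: "Doses may be held as needed until toxicity resolution" (Section 3.5.1), and the Section 7.3 discontinuation reason "Any adverse event (AE) that cannot be adequately managed with dose modifications, including dose interruption > 28 days". Neither supplies a recovery grade or a reduction step. Section 1.5 gives any-grade paresthesia on monotherapy as 25.4% of 185 (0.254 × 185 ≈ 47 subjects) and no Grade ≥ 3 rate.

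**6. A related ambiguity.** Both QTc texts resume a drug-related case one level lower, and repotrectinib reductions follow Table 2. The repotrectinib doses there are 160 mg QD/BID (Levels 3, -2b, -3b), 160 mg QD (2, -2a, -3a) and 120 mg QD (1, -2, -3).

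- Level 1 to -2: repotrectinib 120 − 120 = 0 mg change; trametinib 2 to 1.0 mg.
- Level -2 to -3: repotrectinib 120 − 120 = 0 mg change; trametinib 1.0 to 0.5 mg.

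Footnote 1 of Table 4 states a floor only at Level -3.

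**The case against.** The strongest reply is that the documents largely settle the QTc question themselves. The restart sentence in Section 6.13.1 cites Table 4, and Section 3.5.1 assigns resumption criteria to Table 4. Section 3.5.1 also applies beyond DLTs, Cycle 1 and Phase 1b. It requires follow-up until the Investigator judges recovery adequate, presents Table 4 as general guidance, and provides for discussion with the Medical Monitor. The Safety Review Committee monitors Phase 2. Screening excludes a mean QTc above 470 msec, and a drug-related case resumes at a lower level.

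Most of this stands as mitigation. A reader might infer that later cycles and Phase 2 have no protection beyond the two conflicting texts. The documents do not support that, because the Section 3.5.1 safeguards cover them.

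The reply does not remove the conflict. The citation of Table 4 is attached to the lower-dose instruction, while the msec release sentence stands alone. The Medical Monitor exception in Section 3.5.1 concerns whether a dose reduction is needed, not the grade to which QTc must recover. That Table 4 governs is a reason to correct Section 6.13.1.

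On paresthesia, the intent is easy to guess and the general hold and discontinuation provisions remain. Even so, a guess at intent is not a rule for Grade ≥ 3.

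On the 120 mg doses, a reader might infer that footnote 1 plainly omits a floor at Levels 1 and -2, and that such subjects should stop repotrectinib when a reduction is needed. The documents do not support that. Table 2 lists combination levels, and read as the sequence 1, -2, -3 the footnote is coherent. A lower repotrectinib step is also feasible: capsules are 40 mg, monotherapy was studied from 40 mg QD, and Section 3.2 allows added dose levels.

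**Conclusion.** The QTc conflict holds. For an asymptomatic Grade 3 event (above 500, not above 515 msec) that has come down only to Grade 2, Section 6.13.1 restarts drug and Table 4 holds it. Table 4 is the designated rule for repotrectinib. The overlap at exactly 500 msec at 2 weeks is editorial but real. The paresthesia gap also holds, limited to the missing recovery grade and reduction step at Grade ≥ 3.

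The frequency of either situation cannot be estimated. The documents give no QTc event rate, and the 25.4% for paresthesia is an any-grade monotherapy figure that should not be read as the size of the Grade ≥ 3 gap. The conclusion rests on the protocol's own equation of > 500 msec with Grade 3 and on no outside grading boundary.

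The 120 mg point is no more than an ambiguity. It arises for toxicity clearly attributed to repotrectinib at Levels 1 and -2, where Section 3.5 lets one drug be modified alone but Table 2 offers no lower repotrectinib dose.

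This is a safety-instruction correction worth making. No sample size, alpha or power figure depends on it.

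**What to change.** - **Section 6.13.1, restart:** replace the ≤ 500 msec criterion with recovery to grade ≤ 1 per Table 4.
- **Section 6.13.1, 2-week removal:** state it as QTc still > 500 msec. A subject at Grade 2 at 2 weeks then stays on hold, subject to the 28-day limit in Section 3.5.
- **Table 4, Prolonged QTc row:** add a cross-reference to the removal limits in Section 6.13.1 (> 515 msec, symptomatic, 2 weeks).
- **Table 4, neurologic row:** add paresthesia.
- **120 mg doses:** the sponsor should say what happens when toxicity clearly due to repotrectinib calls for a reduction at Level 1 or -2, for example by a lower repotrectinib step or by discontinuation. Mandatory discontinuation is not proposed here.

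The cost is wording in one section and one table. Some subjects will restart later, and one who stays at Grade 2 beyond 28 days would meet the existing discontinuation limit, with the clinical-benefit exception in Section 7.3.

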6.13.2. Echocardiogram/MUGA Scan

To monitor potential left ventricular ejection fraction dysfunction, an echocardiogram or multigated acquisition (MUGA) scan will be performed at timepoints specified in the Schedule of Activities ([Table 1](#)). The same method of evaluation should be utilized throughout the study.

6.14. Pharmacokinetics

For the determination of study drug (i.e., repotrectinib and trametinib) plasma concentrations, 5 mL of blood will be collected for each PK sample. Plasma PK samples will be analyzed using a validated bioanalytical method at a Good Laboratory Practice (GLP) compliant bioanalytical laboratory designated by the Sponsor.

Blood samples for PK assessments during the Phase 1b and Phase 2 portions of the study will be collected as specified in the Schedule of Activities ([Table 1](#)).

Additional PK samples may be collected from subjects when experiencing unexpected and/or serious AEs and the date/time should be documented in the CRFs. In addition, the PK sampling scheme may be modified by the Sponsor pending emerging PK data.

All reasonable efforts will be made to obtain the PK samples at the exact nominal time relative to dosing. However, samples obtained within 10% of the nominal time (e.g., within 6 minutes of the 60-minute sample) from dosing will not be considered as a protocol deviation, and the exact time of the sample collection noted on the source document and data collection tool (e.g., CRF).

For the PK samples collected, after sample analysis, the remaining samples may be used for the purposes of exploratory metabolite scouting and potential exploratory protein biomarker testing.

Details regarding the collection, processing, storage, and shipping of the PK samples will be provided in the Study Manual.

6.15. Pharmacodynamics/Biomarkers

In all subjects, blood samples for circulating cell-free DNA (ccfDNA) will be collected at Screening, Cycle 3 Day 1 (in conjunction with tumor assessment evaluation), and either at the time of radiographic disease progression or at the EOT (whichever occurs earlier) as specified in the Schedule of Activities ([Table 1](#)).

Circulating cell-free DNA (ccfDNA) will be isolated from blood to study changes of circulating tumor levels (i.e., assessed by modulations of minor allele frequency [MAF] of genomic alterations), and explore resistance mechanisms as well as clonal evolution.

Blood will be collected across two 10 mL Streck Cell-Free DNA Blood Collection Tubes (for ccfDNA analysis). Circulating cell-free DNA (ccfDNA) will be isolated from blood.

Details for handling of these specimens including processing, storage, and shipment will be provided in the Laboratory Manual.

6.16. Tumor Assessments

Imaging studies will include a computerized tomography (CT) or magnetic resonance imaging (MRI) scan of the brain, chest, abdomen, pelvis. For subjects diagnosed with primary brain tumors, only the MRI of the brain will be required at Screening and during the study.

Tumor assessments will include all known or suspected disease sites and will be performed per specified timepoints according to the Schedule of Activities ([Table 1](#)). For all tumor assessments, the method of assessment that was used at Screening should be the same method used throughout the study. Tumor assessment will be assessed locally by Investigator and by BICR.

For all subjects, radiographic confirmation of objective tumor response or disease progression will be based on RECIST v1.1 and assessed locally by Investigator ([Section 6.16.4](#)).

At the EOT visit, the subject must undergo an EOT tumor assessment evaluation CT or MRI (if more than 4 weeks have passed since the last imaging assessment) to evaluate for radiologic disease progression if treatment is being discontinued for an alternate reason other than confirmed radiographic disease progression.

For subjects demonstrating radiographic response (PR or CR) during treatment, subject responses will be confirmed \geq 4 weeks later (ideally, the confirmation scan should be scheduled at end of the next cycle, i.e., 28 days) after the initial documentation of response by the Investigator.

For subjects discontinuing study treatment before documented radiographic progression, tumor assessments should continue at the current scan interval at the time of treatment discontinuation until radiographic evidence of disease progression, the start of a subsequent anticancer therapy, withdrawal of consent, or decision to no longer treat (e.g., supportive care only), whichever is first.

For subjects discontinuing the study treatment due to documented radiographic progression, survival status will be obtained via a phone call or medical chart review, including information

about subsequent anticancer therapies (including best response) every three months until death, loss of follow-up, or withdrawal of consent, whichever comes first.

6.16.1. CT/MRI of Chest/Abdomen/Pelvis

Intravenous (IV) contrast is required when not medically contraindicated. Subjects who have a contraindication to IV contrast may have MRI exams of the abdomen, and pelvis performed in lieu of CTs and a non-contrast CT of the chest. Positron emission tomography (PET)/CT may be used to document baseline and new disease, but the CT portion of a PET/CT may not be used in lieu of a diagnostic CT, unless it is performed with IV contrast. Additional requirements are provided in the Imaging Manual.

Every effort should be made to maintain the assessment scheduling relative to Cycle 1 Day 1, regardless of any dosing interruptions.

6.16.2. Brain CT or MRI

At Screening, a CT/MRI of the brain should be obtained to rule out newly diagnosed, untreated brain metastases or to document stability of previously treated brain metastases.

CT/MRI brain scans should be performed at every on-study tumor assessment for subjects with brain metastases.

6.16.3. Bone Scan

At Screening, a bone scan should be obtained if bone metastases are suspected. For subjects with bone metastases at baseline, a bone scan should only be repeated to check for residual disease when assessing for complete response unless the bone scan is used to determine RECIST v1.1 response assessment. The bone scan should be performed at the same time as the chest, abdomen and pelvis CT (C/A/P) scans. If a bone scan has been performed within 28 days prior to Cycle 1 Day 1 the scan can be used for Screening. Radiographic confirmation of objective tumor response or disease progression will be based on RECIST v1.1. The same imaging modality should be used at Screening and on study.

